7.4. Adverse events of emtricitabine and emtricitabine/tenofovir

Emtricitabine alone or in combination with tenofovir coformulated as Truvada (emtricitabine 200 mg/tenofovir DF 300 mg) has not been approved for the treatment of chronic hepatitis B. Emtricitabine belongs to a class of anti-HIV drugs (nucleoside reverse transcriptase inhibitors). The most common side effects seen in $\geq 10\%$ patients treated with emtricitabine in combination with other anti-HIV drugs are: headache, diarrhea, nausea, and elevation in creatine kinase. These side effects were generally mild to moderate in severity.

Lactic acidosis (increase in lactic acid) is a very serious reaction, which is characterized by symptoms of nausea, vomiting, abdominal pain, general discomfort and tiredness that do not get better and also by severe hepatomegaly (enlargement of the liver) with steatosis (fatty deposits). Lactic acidosis, including fatal cases, has been reported with the use of nucleoside and nucleotide reverse transcriptase inhibitors.

For people who are infected with HIV as well as hepatitis B, other possible risks of treatment with Truvada include making their hepatitis B worse. The potential risk relates to HBV flares induced by the discontinuation of Truvada and careful monitoring is required when the drug is stopped. There is no evidence of drug-drug interactions when emtricitabine and tenofovir are used in combination.

Truvada dosing is based upon CrCL

Creatinine clearance will be calculated by the MDRD method in all participants prior to initiating therapy and at each study visit to determine Truvada dose.

- Participants whose calculated creatinine clearance decreases to <50 ml/min should have this value confirmed within 72 hrs. If confirmed to be 30-50 ml/min, the dosing frequency for Truvada should be adjusted from every 24 hours to every 48 hours until the calculated creatinine clearance returns to >50 ml/min.
- Participants whose calculated creatinine clearance decreases to <30 ml/min, will discontinue Truvada. Subsequent management will be at the discretion of the investigator, alternative antiviral therapy should be considered and the participant monitored until creatinine clearance returns to baseline or stabilizes.

7.5. Pregnancy

Female participants will be asked to practice effective birth control while they are taking antiviral agents in this study. However, given the very long duration of therapy and the fact that many of the participants are expected to be females of child bearing potential, the following precautions will be taken:

All female participants of child bearing potential will undergo a urine or serum pregnancy test prior to starting therapy and every visit during the peginterferon treatment phase. If a participant is found to be pregnant, therapy will be adjusted as follows:

- Peginterferon alfa-2a will be permanently discontinued
- Tenofovir DF can be continued throughout the pregnancy at the discretion of the study physician.
- Emtricitabine/tenofovir (Truvada) can be continued throughout the pregnancy at the discretion of the study physician.

The study will collect data on the outcomes of any pregnancies that occur in females who conceived while taking study medication.

7.6. Adverse events – definition and management

7.6.1. Definitions

An adverse event (AE) is any adverse change from the participant's baseline (pre-treatment) condition, including intercurrent illness which occurs during the course of the trial, after the consent form has been signed, whether the event is considered related to treatment or not.

The Common Terminology Criteria from the National Cancer Institute (NCI) of the National Institutes of Health will be used for grading severity of AEs. For AEs not outlined in the Common Terminology Criteria, study specific definitions will be identified in the Manual of Operation (MOP).

Serious Adverse Event:

A serious adverse event is an untoward medical occurrence that results in any of the following:

1. Death
2. Is life threatening (risk of death at the time of the event)
3. Requires in-patient hospitalization or prolongation of existing hospitalization
4. Results in persistent or significant disability/incapacity
5. Congenital abnormality or birth defect

Important medical events that do not result in one of the events listed above may be considered a serious adverse event when, based upon appropriate medical judgment, they may jeopardize the participant and may require medical or surgical intervention to prevent one of the outcomes listed above.

A serious adverse event which is unexpected and is related will require expedited reporting to the DCC and the NIDDK and appropriate oversight committees or entities.

Disease related outcomes, such as the following events, will not be considered to be serious adverse events:

1. Development of HCC
2. Hepatic decompensation

Although pregnancy, overdose, cancer (excluding HCC), and potential drug induced liver injury (DILI) are not always serious by regulatory definition, these events must be handled as SAEs.

Unexpected:

An adverse event that is not listed in the Investigator's Brochure (or package insert) or is not listed at the severity that has been observed.

Suspected Adverse Reaction:

Any adverse event for which there is a reasonable possibility that the drug caused the adverse event (i.e., there is evidence to suggest a causal relationship between the drug and the adverse event).

SAE Reporting:

This trial will be conducted under U.S. IND. Therefore, the safety data required to meet IND regulatory requirements will be collected through adverse event reporting by the clinic investigators and will be provided by the Data Coordinating Center to the NIDDK for transmission to the FDA.

A serious adverse event which is unexpected and is drug related (even remotely) will require expedited reporting to the drug manufacturer, the DCC and to local IRB/REBs (per local IRB/REB policy).

Only serious and unexpected suspected adverse reactions with evidence of a causal relationship to the study and/or study drug will be reported to the FDA as an IND safety report according to 21 CFR 312.32.

Unexpected fatal or life-threatening suspected adverse reactions must be reported to FDA no later than 7 calendar days after the sponsor's initial receipt of the information.

All other unexpected serious suspected adverse reactions must be reported to FDA no later than 15 calendar days after the sponsor's initial receipt of the information.

A summary of adverse events will be reported to the FDA as part of the IND annual report.

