2.2.3. Sustained off treatment (36 and 48 weeks after end of treatment) responses

- a. ALT \leq 38 U/L (males), \leq 25 U/L (females) corresponding to approximately 1.25 xULN.
- b. HBV DNA $<$ 1000 IU/mL.
- c. HBV DNA $<$ 1000 IU/mL AND ALT \leq 38 U/L (males), \leq 25 U/L (females) corresponding to approximately 1.25 xULN.
- d. HBV DNA $<$ 20 IU/mL (LLOQ of COBAS Ampliprep/COBAS TaqMan HBV v2.0 test).

2.2.4. Sustained off treatment (36 and 48 weeks after end of treatment) responses in participants with low end of treatment HBsAg levels ($<$ 2000 IU/mL) versus participants with high end of treatment HBsAg levels (\geq 2000 IU/mL)

- a. Cumulative HBsAg loss.
- b. HBeAg loss.
- c. HBsAg seroconversion.
- d. HBeAg seroconversion.
- e. ALT normalization (males \leq 30 U/L, females \leq 20 U/L).
- f. HBV DNA $<$ 1000 IU/mL.
- g. HBV DNA $<$ 20 IU/mL (LLOQ of COBAS Ampliprep/COBAS TaqMan HBV v2.0 test).

2.2.5. Sustained off-treatment (36 and 48 weeks after end of treatment) responses in participants with a substantial drop of HBsAg levels (\geq 1 log from baseline to end of treatment) versus participants who did not have substantial drop of HBsAg levels ($<$ 1 log from baseline to end of treatment)

- a. Cumulative HBsAg loss.
- b. HBeAg loss.
- c. HBsAg seroconversion.
- d. HBeAg seroconversion.
- e. ALT normalization (males \leq 30 U/L, females \leq 20 U/L).
- f. HBV DNA $<$ 1000 IU/mL.
- g. HBV DNA $<$ 20 IU/mL (LLOQ of COBAS Ampliprep/COBAS TaqMan HBV v2.0 test).

2.2.6. Sustained off-treatment (36 and 48 weeks after end-off treatment) responses in participants with end of treatment HBsAg level $<$ 2000 IU/mL and HBV DNA below 1000 IU/mL versus participants with end of treatment HBsAg levels \geq 2000 IU/mL and HBV DNA \geq 1000 IU/mL

- a. Cumulative HBsAg loss.
- b. HBeAg loss.

- c. HBsAg seroconversion.
- d. HBeAg seroconversion.
- e. ALT normalization (males \leq 30 U/L, females \leq 20 U/L).
- f. HBV DNA $<$ 1000 IU/mL.
- g. HBV DNA $<$ 20 IU/mL (LLOQ of COBAS Ampliprep/COBAS TaqMan HBV v2.0 test).

2.2.7. Treatment failure- Cumulative rates of primary nonresponse, partial virologic response and confirmed virologic breakthrough

2.2.8. Rate of discontinuation of treatment due to adverse events.

2.2.9. Rates of adverse events and serious adverse events.

3. Study design

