5.3.3. Safety

As with standard alpha interferon, treatment with peginterferon alfa-2a is associated with many troublesome and occasionally serious, or even life-threatening, side effects. Dose discontinuation has been reported in 6% to 9% and dose modification in 31% to 47% of participants treated in the peginterferon alfa-2a registration trials for hepatitis B. The most frequent causes of dose adjustment were laboratory abnormalities such as

thrombocytopenia or leukopenia. These side effects are particularly common in patients with advanced liver disease and hypersplenism. Peginterferon alfa-2a is contraindicated in participants with decompensated cirrhosis due to the possibility of serious infections, flares of disease, and worsening decompensation. In this study, patients with any clinical or laboratory features suggestive of hepatic decompensation will not be enrolled.

The majority of clinical experience in the use of peginterferon alfa-2a has been in chronic hepatitis C in which peginterferon is combined with ribavirin. In the few studies of peginterferon alfa-2a in chronic hepatitis B it has appeared that side effects are less frequent than in chronic hepatitis C. The overall incidence of serious adverse events was less in studies in hepatitis B (4%-5%) than in those with hepatitis C (7% to 16%), and fewer drug withdrawals were reported (6% to 8% versus 17% to 33%, respectively) despite similar doses and durations of therapy. Depression was also less frequently reported in studies done in hepatitis B (4%) than hepatitis C (22%, $p < 0.001$).

Peginterferon should be avoided in participants with other serious co-morbid illnesses, including, but not limited to, coronary artery disease, cerebrovascular disease, serious autoimmune conditions and severe depression.

Pregnancy:

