8.3. Safety analysis

8.3.1. Adverse events

Summaries of adverse events (number adverse events, number and percentage of participants with adverse events, rates per person-years) will be provided by treatment

group. Events will be summarized based on the date of onset for the event. A treatment emergent adverse event will be defined as an adverse event that begins on or after the date of first dose of study drug. Events that occur prior to the first dose of study medication or after the last dose of study medication will be summarized separately. Summaries of the following are planned:

- all adverse events recorded between screening and first dose of study medication,
- all treatment emergent adverse events,
- all emergent and related adverse events,
- all treatment emergent renal adverse events,
- all treatment emergent and related renal adverse events
- combined Grade 2, 3 and 4 treatment emergent adverse events,
- combined Grade 2, 3 and 4 related treatment and emergent adverse events,
- combined Grade 3 and 4 treatment emergent adverse events,
- combined Grade 3 and 4 related treatment and emergent adverse events,
- all adverse events that caused permanent discontinuation of study drug,
- all adverse events that caused temporary interruption of study drug,
- all serious adverse events, and
- all serious and related adverse events.

In addition quarterly safety analysis will be reported to DSMB.

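### Section 7.6.1 keeps hepatic decompensation and HCC out of the serious adverse events even when they are serious, and does not say how to classify a decompensation that may be drug-induced, so the by-arm SAE comparison can undercount serious liver events

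*Combined protocol and SAP*

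**What the plan says.** Section 7.6.1 of the combined protocol and SAP lists the usual seriousness criteria: death, threat to life, hospitalisation, disability and congenital abnormality, plus important medical events by judgement. It then carves out two outcomes, HCC and hepatic decompensation: "Disease related outcomes, such as the following events, will not be considered to be serious adverse events". The next sentence goes the other way for a neighbouring event. Among other items, "potential drug induced liver injury (DILI) are not always serious by regulatory definition, these events must be handled as SAEs".

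Other sections bear on the same events:

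- **Definition of decompensation.** Sections 6.13.1 and 7.1 use total bilirubin of at least 2.0 mg/dL with direct bilirubin of at least 1.0 mg/dL, or any clinical decompensation. Cause plays no part. Section 6.13.1 refers specifically to decompensation while on peginterferon.
- **Deaths.** Section 7.6.3 puts every death on the Serious Adverse Event form, without exception.
- **Endpoint.** Section 2.2.9 is "Rates of adverse events and serious adverse events".
- **Safety tables.** Section 8.3.1 plans summaries by treatment group. They include "all serious adverse events, and" serious and related events, "combined Grade 3 and 4 treatment emergent adverse events", and "all adverse events that caused permanent discontinuation of study drug". Renal events have two rows of their own. Decompensation, HCC and hepatitis flares have none.

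**The concern.** The trial weighs a possible gain in HBsAg loss against the added harm of 24 weeks of peginterferon. The SAE comparison is one of the summaries a reader will use for the harm side. As defined, it cannot count a participant hospitalised with decompensation or HCC as having had a serious event, unless the decompensation is instead recorded as potential DILI.

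That choice of label rests on the investigator's view of cause. The documents describe no blinding, and only one arm injects peginterferon, so attribution could differ between arms in either direction. SAE counts are likely to be small, so a few differently labelled events could visibly change the comparison.

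**Working it through.** **Classification under the text as written.** Take a participant on study drug with total bilirubin of at least 2.0 mg/dL and direct bilirubin of at least 1.0 mg/dL who is admitted to hospital.

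1. By 6.13.1 or 7.1 this is hepatic decompensation, whatever the cause.
2. By the hospitalisation criterion in 7.6.1 it would be serious.
3. By the carve-out in 7.6.1 it is not an SAE if regarded as a disease-related outcome.
4. By the DILI sentence in 7.6.1 it must be handled as an SAE if regarded as potential drug injury.
5. No text settles the choice between 3 and 4. Section 7.6.2 leaves relatedness to the investigator, using guidelines in the Manual of Operations (MOP), which is not among the documents.
6. If the participant dies, 7.6.3 requires the SAE form, although 7.6.1 says the decompensation is not an SAE.

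HCC differs at step 4. Section 7.6.1 excludes it expressly from the cancers handled as SAEs, so its classification is consistent. It is simply absent from the SAE count.

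**Where the event is still visible.** The general definition opens "An adverse event (AE) is any adverse change from the" participant's baseline condition and applies whether or not treatment is the cause, so decompensation and HCC remain adverse events. They can enter the all-AE row, the Grade 3 and 4 row and the permanent-discontinuation row. On-treatment decompensation can also enter endpoint 2.2.8, discontinuation due to adverse events. These summaries pool all causes and do not isolate liver events.

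**Size, for illustration only.** The plan states no figure that depends on this point, so there is none to reproduce. Inputs:

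- 188 participants per arm (sample size section).
- SAE incidence of 4% to 5%, cited in 5.3.3 from peginterferon studies in hepatitis B.
- Decompensation risk of 0.5% to 3% per arm. This is an assumption; the documents give no rate.

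Expected SAEs per arm: 188 × 0.04 = 7.5 and 188 × 0.05 = 9.4.

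Expected decompensations per arm: 188 × 0.005 = 0.9 and 188 × 0.03 = 5.6.

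Assume that all these decompensations meet a seriousness criterion and that none is already in the cited SAE rate. With d the decompensation risk and s the SAE rate, the share of an arm's serious events left out is d / (s + d):

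| d | s = 4% | s = 5% |
|---|---|---|
| 0.5% | 0.005/0.045 = 11% | 0.005/0.055 = 9% |
| 3% | 0.03/0.07 = 43% | 0.03/0.08 = 38% |

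**The case against.** The strongest reply is that 7.6.1 separates events by presumed cause: disease outcomes on one side, possible drug injury on the other. A reader might infer that the two sentences contradict each other. They do not, strictly. What is missing is the rule for an event that could be either. The MOP, which holds the relatedness guidelines, or the DSMB Charter may supply it. Section 7.6.1 itself refers to the MOP only for definitions of events outside the Common Terminology Criteria.

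A reader might also infer that decompensation drops out of the safety comparison altogether. It does not. Besides the pooled summaries, it is a discontinuation criterion, and more than one clinical case in weeks 192 to 240 pauses further treatment withdrawal (9.1). Section 6.14.1 also says its post-treatment flare and relapse definitions will be used for data analyses. These points stand, but none gives a by-arm count of decompensation or HCC.

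Nor do the documents support calling decompensation the main liver risk. The words "serious infections, flares of disease, and worsening decompensation" in 5.3.3 explain why peginterferon is contraindicated in decompensated cirrhosis, and such patients are not enrolled. For stopping treatment, 7.3.a highlights exacerbation of hepatitis, which is not excluded from SAEs.

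Finally, it is tempting to say the omission could reverse the conclusion on harm. Suppose 9 SAEs are reported in each arm and three omitted decompensations all belong to one of them. The counts become 12/188 = 6.4% against 9/188 = 4.8%, with a Fisher exact p of 0.65. That scenario is assumed, and even so it does not establish a difference between arms.

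**Conclusion.** The concern holds as a defect in the SAE definition and in the SAE comparison built on it. Decompensation and HCC that meet the seriousness criteria are excluded by rule. A decompensation that might be DILI is in or out according to attribution, with no blinding described, and no dedicated endpoint or table row recovers these events by arm. Section 7.6.3 adds an unreconciled case for deaths from decompensation.

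The size is uncertain. Under the assumed 0.5% to 3%, about 1 to 6 decompensations per arm set against about 7.5 to 9.4 SAEs would mean that 9% to 43% of an arm's serious events are uncounted. This rests on an assumed rate, on every such event being serious and left out, and on an SAE incidence taken from peginterferon studies and applied to both arms of a 240-week trial in which one arm receives peginterferon for 24 weeks and the other receives none. The point affects how safety is reported; no power or efficacy figure depends on it.

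**What to change.** 1. In 7.6.1, reconcile the disease-outcome and DILI sentences so that a liver event meeting both has one classification, and align 7.6.3 for deaths from decompensation. If the MOP already holds the rule, cite it there.
2. In 8.3.1, add rows by treatment group for all hepatic decompensation and all HCC events, regardless of SAE label, and for the flares defined in 6.12 and 6.14.1.
3. Alongside the SAE row, report a by-arm count of serious events that includes decompensation and HCC events meeting the seriousness criteria listed in 7.6.1. This also informs the reading of 2.2.9.

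All adverse events already go to the Data Coordinating Center through week 240 or the end of the study (7.6.2), so no new visits or change in treatment are needed. The cost is some wording, a few table rows and slightly higher reported serious-event rates.

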7.6.2. Data collection procedures for adverse events

Participants will be interviewed regarding medical conditions, medication changes, and

symptoms that have occurred at each study visit. An Adverse Event form will be completed if any adverse event is reported. If the Study Coordinator or Principal Investigator learns of any hospitalizations or other adverse events between study visits, an Adverse Event form will be completed. All adverse events and Serious Adverse Events from time of study entry (consent) up to the end of follow-up (week 240 or end of the study) will be reported to the DCC.

A Serious Adverse Event form will be completed for all adverse events rated as serious.

Participants will be followed for all ongoing unresolved adverse events until they are either resolved, or in the opinion of the Principal Investigator, the participant is medically stable.

The investigator will assess the relationship of each adverse event to the use of study drug, based on available information, using guidelines outlined in the MOP.

7.6.3. Reporting procedures

All serious adverse events that are unexpected and related to study drug(s) will be reported to the DCC within 24 hours of knowledge of the event, via the Serious Adverse Event form. This reporting includes serious adverse events that occur from the time the participant has signed the clinical trial consent.

The DCC will distribute the expedited report to the NIDDK, the appropriate oversight committees or entities, and clinical centers. Status reports on serious adverse events will be generated by the DCC and will include the relationship of the adverse event to trial medications, the severity of the event and if the event is resolved or ongoing.

All deaths will be reported to the DCC within 24 hours of knowledge of the death via the Serious Adverse Event form. This reporting begins at the time the participant has signed the informed consent up to the last scheduled participant visit. The report will include the relationship of the death to trial medications. A Clinical Outcome form will also be completed and sent to DCC for distribution. Deaths will be reported immediately to the NIDDK, the appropriate oversight committees or entities, and the clinical centers. A death will be reported as an expedited report only if it is unexpected and drug related. A death must also be reported in accordance with local law and regulations.

The HBRN will comply with Genentech/Roche SAE reporting requirements (see Manual of Operations).

8. Statistical considerations

8.1. Statistical analysis

Summary statistics will be generated to describe the study sample at baseline. Descriptive statistics, including measures of central tendency (e.g. means, medians) and estimates of spread (e.g., standard deviations, quartiles) will be used for continuous variables such as age and baseline HBV DNA and HBsAg levels. Frequency distributions will be used for categorical variables such as HBV genotype and HBeAg status. Ninety-five percent confidence intervals will be calculated for all point estimates of continuous data. Graphical displays (e.g. histograms, box plots) will also be used to describe the data. The baseline demographic information and viral characteristics will be compared between the two treatment arms using the chi-square test for association or exact tests for differences in proportions for categorical variables or using a test of trend

in ordinal data. Continuous variables may be transformed, where appropriate, to meet the assumptions of parametric tests. The Student's t-test or a non-parametric alternative, the Wilcoxon rank-sum test, will be used to determine differences in the distribution of continuous data between the two treatment arms.

Primary analyses will be performed using all enrolled participants (intention-to-treat analysis). Participants will be considered enrolled in the study upon being randomized to one of the two treatment arms.

For all analyses, a p-value of less than 0.05 will be used to indicate statistical significance.

